### **4. Research Materials and Methods:**

The study is planned as a prospective, single-blind randomized controlled randomized study to determine the effect of acupressure on fatigue, quality of life and comfort in hemodialysis patients. This randomized controlled trial will be reported according to CONSORT guidelines and registered on ClinicalTrials.gov (23).

Patients who receive hemodialysis treatment in Adana City Hospital dialysis unit, volunteer to participate in the study and meet the research criteria, will be assigned to the study and control groups according to the days they come for dialysis treatment by lottery method (coin toss). Heads will be determined as the working group and heads will be determined as the control group. Randomization in the study will be done on the website of randomizer.org and patients will be included in the study and control groups with the appropriate randomization method according to the dialysis unit list (12,24).

**NCT Number:** 05892679

The Effect of Acupressure on Fatigue, Quality of Life and Comfort in Hemodialysis Patients. Randomized Controlled Study

The data obtained from the research will be evaluated using appropriate statistical methods. In the analysis of comparative data, parametric or nonparametric tests will be used by evaluating the conformity to the normal distribution. A package program will be used in the statistical analysis of the research.

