#### **4.1. Statistical analysis**

Demographic and patient-reported results in the study will be summarized with descriptive statistics. Continuous, normality checks of measurements will be tested with the Shapiro Wilk test. Differences in repeated measures between groups will be tested with the Repeated Measures test (repeated measure analysis of variance). Bonferroni test will be used for pairwise comparisons. Differences between groups for each measurement will be tested with the Independent Samples t-test. Number and percentage values will be given as descriptive statistics. Pearson chi-square and Fisher Exact chi-square tests will be used for differences between categorical variables. Number and percentage values will be given as descriptive statistics. P<0.05 will be taken as statistical significance.

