**Output:**

Noncentrality parameter <math>\lambda</math>	= 14.000000
Critical F	= 4.0847457
Numerator df	= 1.000000
Denominator df	= 40.000000
Total sample size	= 42
Actual power	= 0.9545279

In the study, 60 hemodialysis patients were randomly assigned to the study and control groups. The study group (n=30) Acupressure is formulated according to the standards of the World Health

[figure not shown]
**NCT Number:** 05892679

Organization and in a certain order to the points of Stomach 36 (St 36), Gall Bladder 34 point (GB 34), Spleen 6 point (SP 6) and Kidney 1 point (K 1) will be applied. Consideration will be given to the appropriate pressure intensity and duration. Since the reactions of individuals will be different from each other, the stiffness and pressure will be adjusted according to the sensitivity of the individual in order not to cause tissue damage. Pressures will be applied manually by a single practitioner. Considering the anatomical area where the point is located, the most suitable thumb, index and/or middle finger will be used for application to the relevant point. Successive compressions will be applied at a frequency that does not disturb the patient, does not cause pain, and has a calming effect.

Considering the studies done, a person will be given acupressure three times a week for four weeks. No intervention will be made to the control group (n=30). In order to avoid ethical problems both groups will be given an informative training on acupressure and fatigue, increase the quality of life and comfort level in hemodialysis patients at the end of the study. The primary outcome of the study is the effect of acupuncture on fatigue in hemodialysis patients. The secondary result of the study is the effect of acupuncture on quality of life and comfort level in hemodialysis patients.

[figure not shown]
[figure not shown]
The results will be collected before the acupressure and in the 4th week of the last intervention.

Table 1. Application Points Used in the Study (33)

Application Site Name	Picture of Application Site	Description of Application Site
Stomach 36. point  (Zusanli: ST 36)		In the leg, it is one finger width lateral to the anterior crest of the tibia, and 3 cuns below the ST 35 in the depression on the lateral side of the patella.

**NCT Number:** 05892679

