## 5. Research Flow Process

The Flow Chart of this research will be completed in three stages and four steps as indicated in Figure 1.

**First Stage (Preparatory Stage):** An internationally approved acupressure certificate was obtained by the researcher in July 2022 (the certificate is in Annex I). The place where the acupressure application will be made will be arranged in accordance with the acupressure application. Necessary materials will be purchased for acupressure application (bed cover, pillow, etc.)

**Second Stage (Implementation Stage):** This stage will consist of four steps.

**In the first step:** In the first step of the application, patients who receive hemodialysis treatment in Adana City Hospital dialysis unit and meet the research criteria and are willing to participate in the research will be given brief information about the research and their verbal consent will be obtained. The fatigue experience VAS scores of the patients who accepted to participate in the study on a voluntary basis will be calculated. Those with a VAS value of fatigue severity  $\geq 4.0$  between 0 and 10 points will constitute the sample of the study.

**In the second step:** Sample selection will be completed in accordance with the inclusion, exclusion and exclusion criteria of the study, and then randomization will be performed. The patients will be informed about the purpose of the research and the research process, and the patients will be asked to fill in the "Piper Fatigue Scale", "Kidney Disease and Quality of Life Form" and "Hemodialysis Comfort Scale" as a pre-test with an informed consent form.

**Third step:** Patients in the study group will be given a total of 12 sessions of acupressure application bilaterally to Stomach 36 (St36), Gall Bladder 34 (GB34), Spleen 6 (SP6) and Kidney 1 (K1) acupuncture points for 4 weeks and 3 days a week for 20 minutes. No intervention will be made to the control group other than routine maintenance during the four-week period.

**Fourth step:** After the 4-week acupressure process is over, after the last acupressure session, the patients in the study group will have the "Piper Fatigue Scale", "Kidney Disease and Quality of Life Form" and "Hemodialysis Comfort Scale" filled face-to-face as a post-test. At the end of 4 weeks, the control group will have to fill in the "Piper Fatigue Scale", "Kidney Disease and Quality of Life Form" and "Hemodialysis Comfort Scale" as a post-test before hemodialysis.

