**Third Stage (Reporting Stage):** At this stage Statistical analysis of the data obtained from the patients will be made and a research report will be written.

**NCT Number:** 05892679

The Effect of Acupressure on Fatigue, Quality of Life and Comfort in Hemodialysis Patients. Randomized Controlled Study

**Figure 1.** Flow Chart of the Research

STAGE 1. PREPARATION STAGE	
Arrangement of Adana City Hospital dialysis unit in accordance with acupressure application in order to perform acupressure application.
		
STAGE 2 IMPLEMENTATION PHASE	1. Step	
Contacting patients receiving hemodialysis treatment in Adana City Hospital dialysis unit, Determining compliance with the criteria, Measuring fatigue experience VAS scores, Recruiting patients willing to participate in the study
	
	2. Step	
Determining the sample according to the criteria Performing the randomization (Study Group; n=30 - Control Group; n=30) Getting Informed Consent and pre-test data collection forms ("Patient Description Form", "Piper Fatigue Scale", "Kidney Disease and Quality of Life Form" and "Hemodialysis Comfort Scale")
	
	3. Step	
Making acupressure group (n=30) apply acupressure for 20 minutes three times a week for four weeks.
	
No intervention in the control group (n=30)

	4. Step	
Having the study group (n=30) fill out the post-test data collection forms ("Piper Fatigue Scale", "Kidney Disease and Quality of Life Form" and "Hemodialysis Comfort Scale") after the last acupressure session, after the 4-week acupressure process is over.
	
The control group to be fill out the post-test data collection forms ("Piper Fatigue Scale", "Kidney Disease and Quality of Life Form" and "Hemodialysis Comfort Scale") at the end of the interview at the end of 4 weeks.

STAGE 3 REPORTING PHASE	
ANALYSIS OF DATA AND WRITTEN RESEARCH REPORT
		

**NCT Number:** 05892679

The Effect of Acupressure on Fatigue, Quality of Life and Comfort in Hemodialysis Patients. Randomized Controlled Study

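### Randomisation is listed before full information, the consent form and the self-reported pre-test, and nothing keeps the arm undisclosed until these are done

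*Combined protocol and SAP*

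**What the plan says.** **Before randomisation.** In the first step of Section 5 (Research Flow Process), patients "will be given brief information about the research and their verbal consent will be obtained", and the fatigue VAS is scored to find those at 4.0 or above.

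**Second step, text.** Sample selection is completed "and then randomization will be performed. The patients will be informed about the purpose of the research and the research process". The same sentence goes on to have patients complete the Piper Fatigue Scale, the kidney disease quality-of-life form and the Hemodialysis Comfort Scale "as a pre-test with an informed consent form".

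**Second step, Figure 1.** The order is the same: "Performing the randomization (Study Group; n=30 - Control Group; n=30) Getting Informed Consent and pre-test data collection forms".

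**Timing of measurement.** Section 4.3, below the sample-size output, says: "The results will be collected before the acupressure and in the 4th week of the last intervention". This places the first measurement before treatment and does not mention allocation.

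**Allocation and blinding.** Section 4 says patients "will be assigned to the study and control groups according to the days they come for dialysis treatment by lottery method (coin toss"). It also describes randomisation through a website applied to the dialysis unit list. The study is called single-blind, but no blinded party or time point is named, and controls receive routine care without a sham.

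**Analysis.** Section 4.1 plans two comparisons that use the pre-test: "Differences in repeated measures between groups will be tested with the Repeated Measures test", and "Differences between groups for each measurement will be tested with the Independent Samples t-test".

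**The concern.** All three outcome scales are self-reported, and fatigue is the primary outcome. There are only two measurements, so the pre-test is half of the data in the repeated-measures analysis. If patients know their arm when they receive the consent form and the scales, two things can go wrong.

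- **Differential refusal.** A patient who knows that the allocation is to no intervention may decline the written form. The groups analysed are then no longer the groups randomised. Verbal consent in step 1 lowers this risk but does not exclude it.
- **A baseline influenced by the arm.** Patients may rate their fatigue differently once they know what they will receive. The direction is unknown, and opposing motives may partly cancel. A net shift that does not fully persist to post-test biases the group-by-time comparison.

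Assignment by dialysis day, if used, would make the arm easy to infer from the patient's own schedule.

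**Working it through.** **1. Order of events.** The text of step 2 and step 2 of Figure 1 agree: sample, randomisation, then consent form and pre-test. Full information as a separate item appears only in the text, also after randomisation. Three places might have supplied a safeguard, and none does:

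- The timing statement in Section 4.3 ties the pre-test to the start of acupressure. A pre-test taken after the arm is known satisfies it.
- The single-blind label in Section 4 names nobody and no time point. With no sham, it cannot serve as a rule against disclosure.
- Neither allocation route in Section 4 describes concealment.

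**2. The plan's own figure, for context.** With f = 0.5, 2 measurements and correlation 0.5, λ = f² × N × m / (1 + (m − 1)ρ) = 0.25 × 42 × 2 / 1.5 = 14.0. On 1 and 40 df this gives critical F 4.0847 and power 0.9545, as Section 4.3 prints. The order of consent, pre-test and randomisation does not enter this calculation.

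**3. Illustration of a shifted pre-test.** From the documents: 30 per arm and correlation ρ = 0.5. Assumed: no true effect, SD 1 at both visits, a net between-group shift b at pre-test of 0.1, 0.2 or 0.3 SD, and a fraction p of it persisting at post-test.

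- Bias in the difference of changes: b(1 − p).
- SD of a change: √(2 − 2ρ) = 1.
- Noncentrality: b(1 − p) / √(2/30), two-sided t on 58 df.
- Example, b = 0.2 and p = 0.5: 0.1 / 0.2582 = 0.387, giving a rejection rate of 6.7%.

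| Fraction persisting | b = 0.1 | b = 0.2 | b = 0.3 |
|---|---|---|---|
| All | 5.0% | 5.0% | 5.0% |
| Three quarters | 5.1% | 5.4% | 5.9% |
| Half | 5.4% | 6.7% | 8.8% |
| None (worst case) | 6.7% | 11.9% | 20.8% |

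A simulation of 100,000 trials agrees: 6.8%, 11.9% and 20.9% with none persisting; 5.3%, 6.7% and 8.7% with half. At b = 0.2 and p = 0.5, a correlation of 0.3 gives 6.2% and 0.7 gives 7.8%.

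**4. The between-groups term.** The sample size was computed for the between-factors test, which compares each patient's mean of the two measurements. With none persisting, the bias is b/2 and the SD of the mean is √((1 + ρ)/2) = 0.866. The error is 5.6%, 7.2% and 10.1%. Here persistence makes matters worse: the bias is b(1 + p)/2, and b = 0.3 with p = 1 gives 26.1%.

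**5. Would the planned pre-test t-test reveal it?** Its noncentrality is b / √(2/30). It is significant in 6.7%, 11.9% and 20.8% of trials, so it misses the shift in about 93%, 88% and 79%.

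**6. Illustration of refusal.** Assume k of 30 controls decline after allocation and differ by 0.5 SD from those who stay. The bias at post-test is (k/30) × 0.5. For k = 3 it is 0.05 SD, and the post-test t-test (30 v 27) has error 5.4%. For k = 6 it is 0.10 SD, and the error (30 v 24) is 6.5%.

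**The case against.** **The order may be loose drafting.** The sentence after randomisation has no time word, and step 2 of Figure 1 is one run of items. Generating a list is not disclosing it. Harm needs disclosure before the pre-test, a net shift, and, for group-by-time, incomplete persistence; none of these is stated. This stands as a limit on how firmly the point can be put. It does not remove the point, because two descriptions give the same order and no rule blocks disclosure.

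**Consent is partly obtained first.** This is true of verbal consent, and the refusal figures rest on assumed numbers and are small in any case.

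**Reordering might not help the group-by-time test.** Patients will know their arm at post-test whatever the order. If the part called persisting is really this open-label reporting, reordering removes only the pre-test shift, and the bias goes from b(1 − p) to bp. At p = 0.75 the error would rise from 5.1%, 5.4% and 5.9% to 5.9%, 8.8% and 13.8%; at p = 0.5 it would not change. This is a fair caution: the table shows errors under the present order, not a guaranteed gain. But if the persisting part is carry-over from the pre-test answers, reordering removes that too, and the between-groups term improves at every p. Relying on a distorted baseline to offset a distorted post-test is not a defensible design.

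**Cost under assignment by day.** Waiting for patients on all dialysis days could leave early pre-tests some time before the first session. This stands as a practical cost.

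**Conclusion.** The concern holds. Both descriptions of step 2 put randomisation ahead of full information, the consent form and the self-reported pre-test, and no rule in the plan keeps the arm undisclosed until these are complete. This is the natural reading of a listed order, not proof that patients will be told early.

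The size cannot be derived from the documents. Under the assumed shifts of 0.1 to 0.3 SD, the group-by-time error stays below 9% if at least half persists and reaches 20.8% only if a 0.3 SD shift vanishes entirely by post-test. A fully persisting shift does not bias group-by-time, though it does bias the between-groups term, and a shift confined to the pre-test leaves the post-test t-test unaffected. The planned baseline test is too weak to serve as a check.

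The effect is modest in most scenarios. The change should be made because it costs little and closes both routes to bias before treatment starts.

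**What to change.** Reword step 2 of Section 5 and step 2 of Figure 1 to this order: eligibility and VAS, full information, signed consent form, pre-test scales, then randomisation and disclosure of the arm. If assignment by dialysis day is kept, make the coin toss only after consent and pre-tests are complete for patients on all days. Which allocation method to use is a separate question.

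Forms, sample size and analysis stay as they are. No extra person is needed, because no allocation exists when consent and pre-test are taken. First sessions may start later, and some pre-tests may be older at the first session, mainly under the day-based toss. If the dates in Section 4.3 bound the whole trial, 30 May to 30 September 2023 is 123 days, or 17.6 weeks; less the 4-week intervention, about 13.6 weeks remain for recruitment, consent and pre-tests.

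The change does not remove open-label reporting at post-test, and the report should say so.

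### The study arm's only post-treatment assessment is tied to the last acupressure session, with no interval and no position relative to dialysis, so the contrast with controls can include a short-lived response to that session

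*Combined protocol and SAP*

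**What the plan says.** Each arm has one pre-test and one post-test on three self-reported scales (fatigue, quality of life, comfort). The timing of the post-test is given in three places.

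- **Section 5, fourth step.** Study arm: "After the 4-week acupressure process is over, after the last acupressure session, the patients in the study group will have the" scales filled in face to face. Control arm: at the end of four weeks, "as a post-test before hemodialysis".
- **Figure 1, step 4.** Study arm: "after the last acupressure session, after the 4-week acupressure process is over". Control arm: "at the end of the interview at the end of 4 weeks", with no mention of dialysis.
- **Section 4.3, text after the G\*Power output.** Both arms: "The results will be collected before the acupressure and in the 4th week of the last intervention".

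On treatment, section 5 (third step) says "Patients in the study group will be given a total of 12 sessions of acupressure application bilaterally", each lasting 20 minutes, three days a week for four weeks. For controls: "No intervention will be made to the control group other than routine maintenance during the four-week period". Section 4.3 says the compressions are to be given at a frequency that, among other things, "does not cause pain, and has a calming effect". The primary outcome, fatigue, is defined there without a time point. No assessment after the post-test is planned.

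**The concern.** The two arms are assessed under different rules. The study arm's post-test is anchored to a treatment session. The control post-test is anchored to the end of four weeks and, in one of the two places, to dialysis. A study patient could therefore fill in the scales minutes after a 20-minute session meant to be calming, while the control patient has had no comparable contact.

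If a session shifts self-reported fatigue or comfort for a few hours, that shift enters the study-arm post-test and has no counterpart in the control arm. With a single post-treatment time point, the data cannot show whether a difference reflects the last session, the four-week course, or both. This matters for how the result is used: section 3 hopes that hospital administrations will adopt the findings as institutional policy, and a reader of such a policy would expect a benefit that outlasts the session.

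Aligning the arms on dialysis alone would not settle the point. A study patient could be treated and then assessed, all before dialysis starts.

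**Working it through.** **1. The timing statements side by side**

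| Place | Study arm | Control arm | Interval since last session | Position relative to dialysis |
|---|---|---|---|---|
| Section 5, fourth step | After the last session, course over | End of 4 weeks | Not stated | Controls only: before |
| Figure 1, step 4 | After the last session, course over | End of the interview, end of 4 weeks | Not stated | Not stated |
| Section 4.3 | Fourth week, relative to the last intervention | Same sentence | Unclear | Not stated |

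The section 4.3 sentence can mean week 4 of the course or four weeks after the last session, so it does not supply the missing interval. No place gives one rule that applies to both arms.

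**2. The plan's own figure**

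Inputs from section 4.3 and the G\*Power input block: f = 0.5, alpha = 0.05, power 0.95, 2 groups, m = 2 measurements, correlation rho = 0.5, between-factors test.

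lambda = f² × N × m / (1 + (m − 1) × rho) = 0.25 × 42 × 2 / 1.5 = 14.0.

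With 1 and 40 degrees of freedom the critical F is 4.0847 and the power is 0.9545, as printed in the plan. N = 40 gives 0.9450, which is below 0.95. The stated 42 (21 per group) is therefore reproduced, and nothing here changes it.

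**3. What a transient shift would do**

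The documents give no size for a session after-effect, so d below is an assumption, in SD units. Suppose the course has no lasting effect and session 12 shifts only the study-arm post-test by d. Take unit SD, rho = 0.5 and n per arm.

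- Post-test t-test: difference d, variance 1, noncentrality d / √(2/n).
- Group-by-time test: the variance of a change is 2(1 − rho) = 1, so the noncentrality and the result are the same as for the post-test t-test.
- Between-groups ANOVA (pre and post averaged): difference d/2, variance (1 + rho)/2 = 0.75, noncentrality (d/2) / √(0.75 × 2/n).

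For n = 30, √(2/30) = 0.2582 and √(0.75 × 2/30) = 0.2236. With d = 0.3, for example, the noncentralities are 0.3/0.2582 = 1.16 and 0.15/0.2236 = 0.67.

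Chance of p < 0.05 (two-sided, noncentral t, 2n − 2 degrees of freedom):

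| d | Post-test t-test, n = 30 | Between-groups ANOVA, n = 30 | Post-test t-test, n = 21 | Between-groups ANOVA, n = 21 |
|---|---|---|---|---|
| 0 | 0.050 | 0.050 | 0.050 | 0.050 |
| 0.2 | 0.119 | 0.072 | 0.097 | 0.065 |
| 0.3 | 0.208 | 0.101 | 0.158 | 0.085 |
| 0.5 | 0.478 | 0.196 | 0.353 | 0.150 |

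The shift enters the post-test difference in full and the between-groups main effect by half. More patients do not remove it; they make it easier to detect.

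**The case against.** Four objections deserve weight.

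- **The interval is unknown, so nothing shows that effects are mixed.** This stands. A reader might infer that the scales are handed out as session 12 ends and that the contrast therefore does mix the two effects. The documents do not say so, and one reading of the section 4.3 sentence puts the assessment four weeks later. What they support is that the plan does not exclude the mixing.
- **The after-effect is conjecture.** This largely stands. The calming phrase describes how the compressions are applied; it is not evidence of a change on any of the three scales. The documents give no recall period for the scales, and a scale that asks about recent weeks would respond less to a single session. An effect on all three outcomes is possible but not shown.
- **The comparison is valid as it is.** This also stands. Session 12 belongs to the regimen, and assessment after it estimates the end-of-treatment effect against routine care. The protocol makes no explicit claim of durability. The difficulty is one of interpretation, if the result is read as a lasting benefit of the course.
- **The percentages look like false-positive rates.** A reader might set 12%, 21% and 48% against 5% and infer inflated type I error. That is wrong. If acupressure shifts the post-test by d, the null hypothesis is false, and these are the chances of detecting a real but possibly brief effect.

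None of this removes the difference in assessment rules between the arms, or the three timing statements that do not agree.

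**Conclusion.** The concern holds as a gap in the assessment rule. The study arm's single post-treatment assessment follows a session that controls do not have, the interval is unspecified, and only controls are given a position relative to dialysis, in one place of two. The plan therefore permits a contrast that cannot tell a short-lived response from a course effect.

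The size is illustrative only. It rests on the assumed shifts, on there being no lasting effect, and on assessment soon enough after session 12 for the shift to be present. The ANOVA figures also use the plan's correlation of 0.5. On those terms, with 30 per arm, the chance of a significant result lies between about 7% and 20% on the ANOVA that sized the trial, and between about 12% and 48% on the post-test t-test. The documents do not establish that an after-effect exists, or that the comparison with routine care is invalid at the end of treatment. The change is worth making because it is cheap and removes an avoidable difference between the arms.

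**What to change.** Reconcile the section 4.3 timing sentence, the fourth step of section 5 and step 4 of Figure 1 to one assessment rule for both arms: the post-test is completed before dialysis at the first dialysis attendance after the four-week period ends, with no acupressure earlier that day, and the interval since the last session is recorded for each study patient. State the same time point in the definition of the fatigue outcome.

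The cost is protocol wording and one recorded item; the sample size is unaffected. The study-arm post-test moves by one dialysis visit. How many days that is cannot be given, because the documents do not state the dialysis frequency; three times a week is the acupressure schedule. A very short-lived benefit would no longer be counted, so the observed effect may be smaller. Nothing in the documents shows how long an after-effect would last, which is why the interval should be recorded.

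Section 4.3 dates the study population from 30 May to 30 September 2023. If the data are already collected, report the actual interval between the last session and the post-test, and limit the conclusion to the effect at the end of treatment.

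### The way the post-test questionnaires are completed is specified unevenly by arm and time point, and nothing keeps the treating practitioner away from the study group's post-test

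*Combined protocol and SAP*

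**What the plan says.** Section 5 (Research Flow Process) describes three collections of the Piper Fatigue Scale, the kidney disease quality-of-life form and the Hemodialysis Comfort Scale.

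- **Pre-test, both arms (Second step):** "the patients will be asked to fill in the" scales. No mode is stated.
- **Post-test, study group (Fourth step):** "after the last acupressure session, the patients in the study group will have the" scales "filled face-to-face as a post-test".
- **Post-test, controls (Fourth step):** "At the end of 4 weeks, the control group will have to fill in the" scales "as a post-test before hemodialysis". No mode is stated.

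Figure 1, Step 4, does not repeat the contrast. For the study group it reads "Having the study group (n=30) fill out the post-test data collection forms", with no mention of face-to-face completion. It uses the same verb for the controls, but places their forms "at the end of the interview at the end of 4 weeks". That interview is not described anywhere else.

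On personnel, Section 4.3 says "Pressures will be applied manually by a single practitioner", and the First Stage in Section 5 says that the researcher obtained an acupressure certificate. No section says who hands out, reads out or collects the questionnaires. The data collection sections list the forms but give no rule for administering them.

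**The concern.** Fatigue is the primary outcome; quality of life and comfort are secondary. All three are self-reported on questionnaires. Controls receive no intervention beyond routine care, so patients know their arm.

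A site that follows the Fourth step to the letter could hold a face-to-face session for the study group only, and only at post-test. The person present could be the one who gave the 12 sessions, because nothing rules this out. If the manner of completion shifts the answers, a shift confined to one arm at one time point goes straight into the group comparison. Neither the repeated measures ANOVA nor the t-tests of Section 4.1 could separate it from an effect of acupressure.

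This is distinct from blinding. Patients cannot be blinded to a no-intervention control, but the way they complete a form can still be made the same in both arms.

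**Working it through.** **1. Wording side by side**

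| Collection | Section 5 text | Figure 1 |
|---|---|---|
| Pre-test, both arms | patients fill in; mode not stated | forms listed; mode not stated |
| Post-test, study group | face-to-face, after the last session | fill out, after the last session |
| Post-test, controls | fill in; mode not stated; before hemodialysis | fill out, at the end of an interview |

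The face-to-face instruction appears once, for one arm at one time point. Timing also differs: one arm is tied to the last acupressure session and the other to dialysis. The documents do not say where the acupressure sessions fall relative to dialysis, so the two times cannot be shown to coincide.

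**2. The plan's own calculation**

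Inputs from Section 4.3 and its G*Power listing: f = 0.5, alpha = 0.05, power 0.95, 2 groups, m = 2 measurements, correlation rho = 0.5, between-factors test.

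lambda = f² × N × m / (1 + (m − 1) × rho) = 0.25 × 42 × 2 / 1.5 = 14.0

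With 1 and 40 degrees of freedom the critical F is 4.0847 and the power 0.9545, as printed. The allowance for loss gives 21 / (1 − 0.30) = 30 per arm. The sample size is not affected by this point; only n and rho are carried forward.

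**3. What an assumed shift would do**

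The documents give no mode effect. Assume no true treatment effect and a spurious shift b, in SD units of a single score, in the study arm's post-test only. Both tests are two-sided at 5% and use the noncentral t distribution with 2n − 2 degrees of freedom.

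- *Post-test t-test (Section 4.1):* noncentrality = b × sqrt(n/2). For n = 30 this is b × sqrt(15), that is 0.387, 0.775 and 1.162 for b = 0.1, 0.2 and 0.3.
- *Between-factors test (as in the sample size calculation):* this compares the mean of the two measurements. A post-test-only shift moves that mean by b/2, and its SD is sqrt((1 + rho)/2) = sqrt(0.75) = 0.866. The shift is scaled by 0.5/0.866 = 0.577, so the noncentralities are 0.224, 0.447 and 0.671.
- *Group-by-time test:* the SD of the change is sqrt(2 × (1 − rho)) = 1 at rho = 0.5, so the result equals that of the post-test t-test.

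| Assumed shift b | Post-test t-test, 30 per arm | Between-factors test, 30 per arm | Post-test t-test, 21 per arm |
|---|---|---|---|
| 0 | 5.0% | 5.0% | 5.0% |
| 0.1 SD | 6.7% | 5.6% | 6.2% |
| 0.2 SD | 11.9% | 7.2% | 9.7% |
| 0.3 SD | 20.8% | 10.1% | 15.8% |

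Section 4.1 does not say which term of the repeated measures ANOVA decides the primary outcome, so both sets of figures are shown.

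**The case against.** The strongest reply is that this is uneven drafting. Filling in a form and doing so face-to-face are compatible: a patient can complete a form with a researcher in the room. Figure 1 uses one verb for both arms, and its interview for controls suggests personal contact there too. The document is loosely worded elsewhere; Section 4.3, for example, calls the intervention acupuncture when stating the outcomes. Consistency could also be met by face-to-face completion in both arms, so self-completion goes beyond what consistency alone requires.

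Most of this stands. A reader might infer that the arms are in fact measured by different modes and that the fatigue comparison is therefore biased. The documents do not support that. They nowhere say that controls complete the forms alone, by post or by telephone, or that items are read aloud to the study group only. A reader might also infer that the practitioner collects the study group's answers, or that face-to-face answers would favour acupressure. Neither is stated.

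What the reply does not remove is the gap itself. If the difference is only wording, the way the primary outcome is collected is still undefined for three of the four arm-by-time collections, and Section 5 and its figure still disagree. Self-completion without the practitioner is preferable to face-to-face completion in both arms because only the study group has a treating practitioner, so a shared face-to-face rule would not by itself make the setting equal.

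**Conclusion.** The point holds as a defect of specification with a possible bias, and the plan should be changed. The mode of completing the three scales is specified unevenly by arm and time point, the text and Figure 1 do not agree, and nothing keeps the practitioner away from the study group's post-test. This can bias all three comparisons; it is not shown that it does.

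Under an assumed post-test shift of 0.1 to 0.3 SD with 30 per arm, the false-positive rate would be about 7-21% for the post-test t-test and about 6-10% for the between-factors test, against a nominal 5%. These figures rest on the assumed shift, on no true effect and, for the second test, on the plan's correlation of 0.5. They show sensitivity to a bias of that size and are not evidence that one exists. The difference in post-test timing between the arms is explicit in the Fourth step and needs the same correction.

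**What to change.** Rewrite the Fourth step, and align the Second step and Figure 1 with it, so that one rule covers both arms and both time points:

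- Patients complete the three scales themselves, without the acupressure practitioner present. Returning the forms in a closed envelope is a simple way to support this.
- A patient who needs help to read or write receives it under the same rule in both arms, from someone other than the practitioner, and has the same mode at pre-test and post-test. The use of help is recorded on the form.
- The interview mentioned for controls in Figure 1 is either defined for both arms or removed.
- The post-test timing is reconciled, so that both arms are measured at the same stated point relative to dialysis.

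The cost is a text edit, a figure edit and, if used, envelopes. No extra visit is needed, although whoever helps a patient takes on a small task. Self-completion may leave a few more blank items than a face-to-face session.
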